## **2.1 PROTOCOL SYNOPSIS**

The protocol synopsis is in [Appendix 1](#). The schedule of assessments is provided in [Appendix 2](#). Of note, the analyses specified in this SAP supersede the analysis plan described in the Protocol.

## **2.2 OUTCOME MEASURES**

### **2.2.1 Primary Efficacy Outcome Measure**

The primary efficacy outcome measure for this study is the time until a patient first requires the Implant refill according to protocol-defined refill criteria.

### **2.2.2 Secondary Efficacy Outcome Measures**

The secondary efficacy outcome measures are as follows:

- Change from baseline in BCVA at Month 9
- Average change from baseline in BCVA over time
- Change from baseline in BCVA over time

- Change from baseline in CFT over time, as assessed on SD-OCT by the central reading center
- Occurrence of Implant clogging

### **2.2.3 Safety Outcome Measures**

The safety outcome measures are as follows:

- Incidence of adverse events of special interest (AESIs): Adverse events (AEs) associated with ranibizumab, the Implant, Implant-associated procedures, and/or ancillary devices
- Incidence of “pre-specified PDS-associated AEs”
- Incidence of ocular and non-ocular AEs and serious adverse events (SAEs)
- Incidence of positive serum antibodies to ranibizumab

### **2.2.4 Pharmacokinetic Efficacy Outcome Measures**

The PK outcome measures related to ranibizumab serum concentration-time data following the Implant insertion and refills are as follows:

- Observed maximum serum concentration ( $C_{\max}$ ) and selected postdose-serum concentrations after Implant insertion and all subsequent refills
- Additional estimated PK parameter values including area under the concentration time curve (AUC), time to maximum concentration ( $t_{\max}$ ), and half-life ( $t_{1/2}$ ) after Implant insertion, and all subsequent refills
- Observed serum concentrations ( $C_t$ ) over time from monthly serum sampling when no refills are administered
- Observed steady-state serum concentration ( $C_{\text{trough}}$ ) prior to refills

In addition, optional anterior chamber (aqueous humor) samples will be collected to assess ocular drug concentration.

### **2.2.5 Exploratory Efficacy Outcome Measures**

The exploratory outcome measures are as follows:

- Treatment emergent macular atrophy in all treatment arms
- The Macular Degeneration Treatment Satisfaction Questionnaire (MacTSQ) score at randomization and at Months 1, 6, 9, and the final or early termination visit for patients who speak English or Spanish
- Time to subsequent Implant refills according to protocol-defined refill criteria
- Number of times a patient meets protocol-specified refill criteria
- Proportion of patients in each Implant arm who first meet the protocol-defined refill criteria prior to and at Months 4, 5, and 6
- Proportion of patients with an improvement of BCVA from baseline of  $\geq 15$  letters over time

- Proportion of patients losing  $\geq 15$  letters in BCVA from baseline over time
- Change from baseline in BCVA over time measured under low luminance conditions
- Changes from screening in total lesion area, area of choroidal neovascularization (CNV) lesion, and CNV leakage over time, as assessed by fluorescein angiography
- Proportion of patients meeting LCE criteria
- Proportion of patients requiring explantation
- Changes in CNV perfusion over time, as assessed by optical coherence tomography (OCT) angiography

## **2.3 DETERMINATION OF SAMPLE SIZE**

This study is exploratory in nature and designed to estimate the time to first refill (TTFR) for each of the PDS treatment arms (10 mg/mL, 40 mg/mL, and 100 mg/mL) enrolling 60 patients in each of the PDS treatment arms. The sample size of approximately 220 randomized patients will be adequate to evaluate the primary objective of the study (see the protocol synopsis in [Appendix 1](#)). Pharmacokinetic/pharmacodynamic (PK/PD) modeling and simulation were performed to inform key assumptions used in sample size calculation. Given the simulation results, the hazard ratio (HR) for comparing the 100 mg/mL arm with the 10 mg/mL arm was estimated to be 0.66 for TTFR. Assuming this HR, a total of at least 125 events from all three Implant arms is expected at the primary analysis time (approximately 85 events in the 10 mg/mL arm and a higher dose arm). With 85 events, this study will have approximately 80% power to detect an HR=0.66 between the two Implant arms using a log-rank test at a one-sided significance level of 15%. No multiplicity adjustment is planned for this Phase II study.

Forty patients in the intravitreal arm are considered sufficient to compare each device arm versus the intravitreal arm in change in BCVA from baseline through Month 9 (assuming an estimated SD=10 letters, a two-sided 80% CI will extend approximately 2.62 letters from the observed mean).

## **2.4 ANALYSIS TIMING**

The planned primary analysis will be conducted after the last patient's Month 9 visit occurs. The final analysis will be conducted following the conclusion of the study. The analysis timing for interim analyses can be found in [Section 4.8](#).

# **3. STUDY CONDUCT**

## **3.1 RANDOMIZATION**

Stratified permuted block randomization was used to assign patients to one of the study treatment arms. The randomization stratification factors are BCVA score ( $\leq 65$  letters vs.  $\geq 66$  letters) and number of prior anti-VEGF intravitreal injections ( $\leq 3$  vs.  $\geq 4$ ). Randomization was performed by the IxRS. Outcomes of the stratification factors used in randomization and outcomes of stratification factors as recorded in Case

Report Forms (CRF) will be compared to examine whether there are mis-stratifications. For analyses, the stratification factors as recorded in IxRS will be used.

### **3.2 INDEPENDENT IMAGE REVIEW FACILITY**

All ocular images will be obtained by trained and certified site personnel at the study sites and forwarded to the central reading center for independent analyses and storage. The staff at the central reading center is masked for the treatment assignment and the location (left vs. right) of the study eye.

### **3.3 DATA MONITORING**

Ongoing review of aggregate safety (including AESIs, SAEs, and adverse device effects [ADEs]) along with key efficacy data (BCVA and refills for benefit-risk assessments) was performed by the Internal Monitoring Committee (IMC). The IMC is composed of two subcommittees: a masked IMC that will meet regularly to review study safety data, study conduct, and operation and an unmasked IMC that will meet as needed to review unmasked safety and/or efficacy data and operational issues. The masked IMC members were granted access to the unmasked interim efficacy analysis results for the purpose of planning future Phase III studies, and continued to review only the aggregate cumulative safety summary in an attempt to provide unbiased assessment. The IMC roles and responsibilities are outlined in the IMC Agreement.

## **4. STATISTICAL METHODS**

### **4.1 ANALYSIS POPULATIONS**

Any site with serious Good Clinical Practice (GCP) non-compliance issues will impact the efficacy and safety assessments for this study. In case of any data falsification or other deviations from GCP, data will be handled as follows:

- Exclude data for summaries of patient disposition, summaries of demographic and baseline characteristics, PK/PD analyses, and all efficacy analyses
- Exclude data for all safety analyses for a clean overall summary
- Additionally, include data for ocular adverse event summaries as sensitivity analyses
- Provide a separate listing of all safety adverse events for non-compliance sites for full disclosure

A directed Roche Quality Assurance audit conducted in November 2017 confirmed serious GCP non-compliance involving fraudulent data collection on the part of multiple staff members (study coordinators) was established at Site [REDACTED], and the FDA was notified of the alleged misconduct on 21 December 2017. Due to the findings identified to date (data falsification), the data for this site will be handled as described above since the Sponsor concluded that the integrity of the data produced at this specific site did not meet requirements for GCP.

#### **4.1.1 Modified Intent-to-Treat Population**

Efficacy analyses will be based on the modified intent-to-treat (ITT) population, which will comprise all patients who were randomly assigned to study treatment and receive at least one study treatment. Patients will be summarized by treatment arm and analyzed according to the treatment actually received and not according to the treatment they were randomized to receive, in the event of a discrepancy. Patients who received an Implant will be considered a PDS patient.

#### **4.1.2 Safety Population**

The safety population will be composed of all patients who received at least one study treatment. Patients will be summarized by treatment arm and analyzed according to the treatment actually received and not according to the treatment they were randomized to receive, in the event of a discrepancy. This population will be used for safety summaries and analyses.

#### **4.1.3 Pharmacokinetic-Evaluable Population**

Pharmacokinetic-evaluable patients will include randomized patients who have received at least one study drug administration and have provided at least one serum and/or aqueous PK sample for determination of ranibizumab concentration. Patients may be excluded from the PK analyses if they have AEs that will interfere with the interpretation of the results. Treatment arms for this population will be defined according to the actual treatment received.

### **4.2 ANALYSIS OF STUDY CONDUCT**

A summary of patient disposition will be presented in the all randomized patient population excluding patients from site [REDACTED] and will include the number of patients randomized, and the number and percentage of patients who completed the study, who received study drug, who discontinued study drug, and who discontinued study participation. The reasons for study/study drug discontinuation will also be summarized. A summary of the number and percentage of patient's eligibility criteria deviations and other major protocol deviations will also be tabulated.

### **4.3 ANALYSIS OF TREATMENT ARM COMPARABILITY**

Demographic and baseline characteristics such as age, sex, race/ethnicity, and baseline disease characteristics (i.e., BCVA and OCT parameters) will be summarized by treatment arm in the modified ITT population using means, standard deviation, medians, and ranges for continuous variables, and counts and proportions for categorical variables, as appropriate.

### **4.4 EFFICACY ANALYSIS**

Efficacy analyses will be done using the modified ITT population. Although this study is powered based on the log-rank test at a one-sided significance level of 15% for the primary outcome measure, there is no prespecified alpha level for other outcome

measures. 95% CIs will be reported for estimation purposes and for treatment arm differences unless stated otherwise. No adjustments will be made for multiplicity. Except for the primary endpoint, no statistical tests will be conducted. All analyses will be based on observed results unless imputation of missing data is specified. For the analysis purpose, the stratification factors as recorded in IxRS will be used if there is a discrepancy between the CRF and the IxRS data.

Unless otherwise specified, continuous variables will be summarized using descriptive statistics including mean, standard deviation, median, and range. Categorical variables will be summarized using counts and percentages.

#### **4.4.1.1 Primary Efficacy Endpoint**

The primary endpoint for this analysis is the time from the day of device implantation until a patient first requires the Implant refill according to protocol-defined refill criteria (TTFR). For patients without any refills prior to or on the cutoff date, TTFR will be censored. The censoring date will be defined as the date of a patient's last visit before the cutoff date or the date when the patient discontinues from the study, whichever occurs first. Observed data will be used for these analyses.

Time to first refill will also be censored for the following patients:

- At the time of an intravitreal anti-VEGF injection in the study eye if administered before the first refill
- At the time the refill criteria cannot be assessed, which is defined as at least two refill variables (BCVA, CFT, or new macular hemorrhage) cannot be evaluated for any reason, or are affected by a clinical reason different from nAMD activity, before the first refill
- At the time of explant

Kaplan-Meier plots will be provided by PDS treatment arm. Median TTFR and corresponding 80% CIs will be calculated for each treatment arm using the Kaplan-Meier method.

To support the dose level selection among the Implant groups, the primary analysis for TTFR will include the following pairwise group comparisons, each with a stratified log-rank test at a one-sided significance level of 15%. The stratification factors to be included are baseline BCVA score ( $\leq 65$  letters vs.  $\geq 66$  letters) and number of anti-VEGF-intravitreal injections ( $\leq 3$  vs.  $\geq 4$ ).

- Implant with 100 mg/mL versus Implant with 10 mg/mL
- Implant with 100 mg/mL versus Implant with 40 mg/mL
- Implant with 40 mg/mL versus Implant with 10 mg/mL

In addition, the HR for each pairwise comparison of the treatment arms will be estimated using a Cox proportional hazards regression model stratified by baseline BCVA score

( $\leq 65$  letters vs.  $\geq 66$  letters) and number of prior anti-VEGF-intravitreal injections ( $\leq 3$  vs.  $\geq 4$ ) with main effects for treatment. Estimated HRs for each pairwise comparison will be presented with the corresponding 70% CIs.

Using the above methods, two sensitivity analyses will be performed. One sensitivity analysis will be done where TTFR will be additionally censored for patients with dosing errors. The other sensitivity analysis will be done where TTFR is defined as the time from day of device implantation until a patient actually received the first Implant refill, regardless whether there is an intravitreal anti-VEGF injection, a visit where refill criteria cannot be adequately assessed, or patients have dosing errors. For patients without any refills prior to or on the cutoff date, TTFR will be censored on the date of a patient's last visit before the cutoff date or the date when the patient discontinues from the study, whichever occurs first.

To assist in the interpretation of TTFR and change from baseline in BCVA, the following figures will be generated:

- Swimmer plots by patient time from first dose of study treatment (ranibizumab filled Implant insertion) to the end of study with a mark for each refill time will be provided by Implant arm to explore the refill pattern.
- Spaghetti plots of change in BCVA and change in CFT over time for each Implant arm showing refill times will be provided to explore the association of refill frequency with BCVA and CFT.

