Starting at the Day 1 visit (ITV treatment arm) or starting at the Month 1 visit (Implant arms), all patients will be contacted by site personnel 3 ( $\pm$ 1) days after each ITV injection or Implant refill to elicit reports of decrease in vision, eye pain, unusual redness, or any other new ocular symptoms in the study eye. Patients in the Implant treatment arms will also be asked to verify whether they have taken the prescribed, self-administered, post-injection antimicrobial treatments. The ITV arm patients' self-administered antimicrobial treatments will be prescribed at the investigator's discretion.

Only one eye will be selected as the study eye during the screening period. If both eyes are eligible, the investigator will determine, during the screening, which eye will be selected for study treatment (study eye).

- Should a non-study (fellow) eye require treatment for nAMD after randomization, treatment with ranibizumab is not recommended within 7 days of the study eye scheduled visit. For patients in the Implant arms, if the fellow eye will be treated 7 days after study eye treatment, ranibizumab should be administered after serum PK sample collection.
- The drug for the fellow eye during the study will be open-label ranibizumab and will be supplied by Genentech (see Section 4.3.1.4 for the drug formulation for the non-study eye). If a change in therapy is clinically indicated for the fellow eye per investigator judgment, the change must be discussed and agreed by the Medical Monitor prior to being made.

All study patients will have scheduled monthly visits during the study. After the Day 1 visit, patients randomized to the Implant treatment arms will be evaluated for their Implant refill at each monthly visit. Patients randomized to the ITV injection arm will be treated at each monthly visit. Study visits will be scheduled to occur according to the schedule of assessments in [Appendix 1](#) and [Appendix 2](#) and have to be relative to the Day 1 (first study treatment) visit date until the patient completes the study.

Each potential study patient can be randomized into the study only once.

Please see Section 5.1.1.1 for the criteria to be used for dose interruption and treatment/study discontinuation. Missed ranibizumab doses will not be replaced.

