## **6.4 EFFICACY ANALYSES**

### **6.4.1 Primary Efficacy Analysis**

The primary endpoint for this analysis will be time to first meeting refill criteria. The primary analyses will be based on data as of 9 months after last patient's entry into the study. For patients without any refills prior to or on the cut-off date of 9 months after LPI, the time of refill will be censored. The censoring date will be defined as the date of a patient's last visit before the cut-off date of 9 months after LPI, or the date when the patient discontinues from the study, whichever occurs first.

The primary analysis population for efficacy is the modified intent-to-treat population defined as all randomized patients who were randomly assigned to study treatment receive study treatment. Patients will be summarized by treatment arm and analyzed according to the treatment actually received and not according to the treatment they were randomized to receive, in the event of a discrepancy.

To support the dose level selection among the Implant groups, the primary analysis for TFR will include the following pair-wise group comparisons, each with a stratified log-rank test at a one-sided significance level of 15%. The stratification factors to be included are baseline BCVA score ( $\leq 65$  letters vs.  $\geq 66$  letters) and number of anti-VEGF ITV injections ( $\leq 3$  vs.  $\geq 4$ ).

- Implant with 100 mg/mL versus Implant with 10 mg/mL
- Implant with 100 mg/mL versus Implant with 40 mg/mL
- Implant with 40 mg/mL versus Implant with 10 mg/mL

In addition, the HR for each pair-wise comparison of the treatment arms will be estimated using a Cox proportional hazards regression model stratified by baseline BCVA score ( $\leq 65$  letters vs.  $\geq 66$  letters) and number of prior anti-VEGF ITV injections ( $\leq 3$  vs.  $\geq 4$ ) with main effects for treatment. Estimated HRs for each pair-wise comparison will be presented with the corresponding 80% CIs.

Kaplan–Meier plots will be provided showing TTFR by implant group. Median time to first meeting refill criteria will be calculated for each treatment arm with the Kaplan Meier method, and the corresponding 80% confidence intervals will also be reported.

- Moreover, for each treatment group, percentage of patients not meeting the protocol-defined first refill criteria by Months 4, 5, 6, 7, 8, and 9, derived from Kaplan-Meier estimates will be provided.

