#### **4.4.1.2 Additional Efficacy Analyses Focused on Refill Times**

The following endpoints will be summarized using descriptive statistics and 80% CIs. These analyses will be done using the modified ITT population observed data.

- Time to subsequent Implant refills according to protocol-defined refill criteria will be estimated using the Kaplan-Meier method.

Time from first refill to the second refill will be analyzed for patients who have undergone the first refill, do not receive an intravitreal anti-VEGF injection in the study eye prior to the first refill, and do not have visits prior to the first refill where refill criteria cannot be adequately assessed.

Time from the first refill to the second refill is defined as time from the date of the first refill to the date of the second refill. For patients who do not have the second refill prior to or on the cutoff date, time to second Implant refill will be censored on the date of a patient's last visit before the cutoff date or the date when the patient discontinues from the study, whichever occurs first.

Time to second Implant refill will also be censored for the following patients:

- At the time of an intravitreal anti-VEGF injection in the study eye if administered before the second refill
- At the time the refill criteria cannot be adequately assessed, which is defined as at least two refill variables (BCVA, CFT, or new macular

hemorrhage) cannot be evaluated for any reason, or are affected by a clinical reason different from nAMD activity, before the second refill

- At the time of explant

Similar approach will be used to define time from the second refill to the third refill, etc.

- Total number of times a patient meets protocol-specified refill criteria and is refilled will be provided over the following time intervals first 5 months, from Month 6 to Month 10, greater than 10 months
- Patient listing of dosing errors and refill time errors
- Percentage of patients not meeting the protocol-defined first refill criteria over time, derived from Kaplan-Meier estimates

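### The primary TTFR event is meeting the refill criteria, but censoring is keyed to receiving a refill, so a patient who met the criteria and was never refilled is both an event and censored

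*SAP*

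**What the plan says.** SAP 4.4.1.1 measures TTFR from implantation "until a patient first requires the Implant refill according to protocol-defined refill criteria (TTFR"). The administrative censoring rule that follows uses another condition: "For patients without any refills prior to or on the cutoff date, TTFR will be censored". The censoring date is the last visit before the cutoff or study discontinuation, whichever is earlier.

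Protocol 6.4.1 makes the same pairing. It says "The primary endpoint for this analysis will be time to first meeting refill criteria" and then censors patients who have had no refill by the cutoff, 9 months after the last patient in. The SAP states that it supersedes the protocol's analysis plan, so its wording governs.

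SAP 4.4.1.1 adds three censoring rules:
- "At the time of an intravitreal anti-VEGF injection in the study eye if administered before the first refill";
- at a visit where at least two refill variables cannot be evaluated, or are affected by a cause other than nAMD, again limited to the time before the first refill;
- at explant, with no such limit.

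Elsewhere the SAP keeps need and receipt apart. The second sensitivity analysis runs "until a patient actually received the first Implant refill", and SAP 4.4.1.2 counts the "Total number of times a patient meets protocol-specified refill criteria and is refilled".

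The protocol allows a refill to be withheld. Section 5.1 and Table 6 provide for dose interruption, including at the investigator's discretion. Section 4.5.1 holds the next study treatment after cataract surgery. Section 3.1 adds: "Missed ranibizumab doses will not be replaced".

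**The concern.** The event is a status that IxRS determines at a visit. The censoring condition is a procedure. They separate whenever the criteria are met and no refill follows, and neither document says which prevails.

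TTFR is the only endpoint formally tested, and it supports dose selection. Two programmers following the same section could produce different event counts, Kaplan-Meier curves and medians. The percentage not meeting first refill criteria over time (SAP 4.4.1.2) inherits the ambiguity. Followed literally, the censoring sentence keeps a patient with documented disease activity in the refill-free group until the last visit, which pushes refill-free time upward.

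**Working it through.** **Classification.** Each possible path, read against the definition and the censoring rules:

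| Patient | Under the event definition | Under the censoring rules | Result |
|---|---|---|---|
| Criteria never met, no refill by cutoff | No event | Censored | Agree |
| Criteria met, refilled at that visit | Event | Not censored | Agree |
| Criteria met, refill withheld, refilled later | Event at criteria visit | Not censored as never refilled | Event date unclear |
| Criteria met, no refill by cutoff | Event at criteria visit | Censored at last visit or discontinuation | Conflict |
| Criteria met, not refilled, later injection, unassessable visit or explant | Event at criteria visit | Censored at that later time | Conflict |

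As a hypothetical case, take a patient who meets the criteria at Month 4, is never refilled, and has a last visit at Month 9. The definition gives an event at Month 4. The rule gives censoring at Month 9, which adds 9 − 4 = 5 months of apparent refill-free time.

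**Size for one arm.** With 60 patients per Implant arm (SAP 2.3) and no earlier censoring, moving one patient from event to censored shifts that arm's refill-free percentage by 1/60 = 1.7 percentage points from the criteria visit until the patient is censored.

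**Power.** Inputs from SAP 2.3: HR 0.66, 85 events in a pair of arms, log-rank test, one-sided 15%, equal arms. Schoenfeld's formula is

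power = Φ(√(d/4) × |ln HR| − z₀.₈₅), with |ln 0.66| = 0.4155 and z₀.₈₅ = 1.0364.

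- d = 85: 4.610 × 0.4155 − 1.0364 = 0.879, power 81.0%. This reproduces the stated figure. Freedman's formula requires exactly 85 events and gives 80.3%.
- d = 82 (3 lost, assumed): 4.528 × 0.4155 − 1.0364 = 0.845, power 80.1%.
- d = 80 (5 lost, assumed): 4.472 × 0.4155 − 1.0364 = 0.822, power 79.4%.
- d = 75 (10 lost, assumed): 4.330 × 0.4155 − 1.0364 = 0.763, power 77.7%.

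These figures hold the HR at 0.66, so they assume the lost events are not concentrated in one arm.

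**The case against.** The best defence is that the intended event is clear. Both documents describe it as meeting the criteria, and an actual-refill sensitivity analysis makes sense only if the primary analysis differs from it. On that view the censoring sentence is loose shorthand for having had no event. This has force as evidence of intent. It does not rescue the text, because the sensitivity analysis repeats the same censoring condition, which fits only its own definition.

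The affected group is also narrow, and that part of the defence stands:

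- A reader might infer that every withheld refill creates the conflict. It does not. Criteria are reassessed monthly, several Table 6 holds are explicitly temporary, and a later refill takes the patient out of the never-refilled group.
- A reader might infer that any Table 6 complication qualifies. Every refill criterion, including the Month 1 set, requires the change to be due to nAMD activity (Protocol 3.1.1). Vision loss or thickening from inflammation, infection or a retinal break does not meet it. Other complicated eyes fall under the unassessable-visit, injection or explant rules without ever having met the criteria.
- The planned "Patient listing of dosing errors and refill time errors" might be read as showing that refills were missed after criteria were met. It could equally mean refills given at the wrong time or without criteria, so it is weak support.

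In the other direction, a reader might infer a serious loss of power if the lost events all fell in the 10 mg/mL arm. Assume 47 of the 85 events occur there, 4 are lost, and the HR scales to 0.66 × 47/43 = 0.72. Power at 81 events is then about 67%. The documents give neither that split nor any reason to expect that concentration, so this is an illustration only.

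**Conclusion.** The point holds as an inconsistency in the primary endpoint rule. The definition and the censoring sentence give opposite results for a patient who met the criteria because of nAMD activity and had no refill by the cutoff. For a patient refilled later, only the event date is open. The injection, unassessable-visit and explant rules can likewise remove an event that has already happened.

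The number of such patients is not in the documents and is probably small. The losses of 3 to 5 events are assumed. On them power is 80.1% to 79.4% against 81.0%, so the sample-size statement is not in error. What remains is a literal rule that drops true primary events, with a possible upward bias in refill-free time in any arm where this occurs.

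**What to change.** Revise SAP 4.4.1.1, as an analysis change only, with no change to treatment rules:

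1. Date the event at the first visit where IxRS determined that the refill criteria were met, whether or not a refill was given.
2. Censor at the last visit or discontinuation only patients with no such visit by the cutoff.
3. Apply the injection, unassessable-visit and explant rules only when they occur before that visit. Changing the administrative censoring sentence alone would leave these three able to censor after the event.
4. Keep the actual-refill sensitivity analysis as written.
5. Report by arm the number who met the criteria without a refill.

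This needs a short SAP revision. Sites already contact IxRS at the monthly visits, so no new data are required. The small cost is a reconciliation of IxRS determinations with refill records, with a stated rule for any determination found to be erroneous.
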